## **2. Objectives**

### **2.1 Primary Objective**

- To investigate the antiviral activity of AT-752 versus placebo in terms of reduction of DENV RNA from baseline in adult subjects with confirmed DENV infection

### **2.2 Secondary Objectives**

- To evaluate the safety of AT-752 versus placebo in adult subjects with confirmed DENV infection
- To evaluate the PK of AT-752 (**CCI** [REDACTED]) and metabolites in adult subjects with confirmed DENV infection

## **2.3 Exploratory Objectives**

- To describe the effect of AT-752 on viremia (viral titre), DENV nonstructural protein 1 (NS1) levels, fever, and biomarkers (see list in [section 12](#)) compared to placebo in adult subjects with confirmed DENV infection

## **3. Study Design**

### **3.1 Overall Study Design**

This study will enroll approximately 60 subjects in 3 cohorts who meet the inclusion/exclusion criteria. Following screening and informed consent, eligible subjects will be randomized (3:1) to receive either AT-752 or matching placebo either twice a day (BID) or 3 times a day (TID) for 5 days. The dose level for Cohort 1 has been determined on review of PK and safety data from the phase I healthy volunteer study (Protocol AT-02A-001). Specific doses for Cohort 2 and Cohort 3 will be endorsed by a Safety Review Committee (SRC) after an unblinded review of the previous cohorts.

- Cohort 1: 750 mg AT-752/placebo TID for 5 days
- Cohort 2: up to 1000 mg AT-752/placebo BID or TID for 5 days
- Cohort 3: up to 1500 mg AT-752/placebo BID for 5 days

Each cohort will include 20 subjects (15 subjects receive AT-752 and 5 subjects receive placebo). Randomization will be stratified by geographic region. Randomization and the initial dosing should occur on the same day as screening, if possible. Initial dosing should occur no later than 24 hours after screening. Subjects will be discharged on Day 6 (after end of treatment) if hospitalized, and asked to return on Day 7, Day 8, and Day 14 ( $\pm$  1 day) with a final safety follow-up performed on Day 28 ( $\pm$  3 days). For clinical sites that decide to use mobile nursing, some of the subsequent visits (Days 24-5, Days 7-8, and Day 14) may be performed at investigator discretion through mobile nursing. The Day 1, Day 6, and Day 28 visits must be conducted at the clinical site. The maximum duration that any patient will be on study is 32 days.

### **3.2 Study Endpoints**

#### **3.2.1 Primary Endpoint**

The primary objective will be assessed by change in DENV viral load (DENV RNA as measured by RT-qPCR) from baseline.

### 3.2.2 Secondary Endpoints

Secondary endpoints corresponding to secondary objectives (Section 2.2) are:

Secondary objective	Secondary endpoints
Safety	
 
Incidence and grade of any treatment-emergent adverse events (TEAEs) from first dose through Day 28 or withdrawal from the study
 
Incidence and grade of any serious adverse events (SAEs) through Day 28 or withdrawal from the study
 
Vital sign measurements
 
Physical examination findings
 
Clinical laboratory (serum chemistry, hematology, coagulation, and urinalysis) findings
 
Electrocardiogram (ECG) findings
 

Plasma PK of AT-281 and metabolites	
 
Plasma concentrations of [REDACTED] and metabolites (AT-551, AT-229, AT-219, and AT-273) and derived PK parameters (<math>AUC_{last}</math>, <math>AUC_{tau}</math>, <math>C_{max}</math>, <math>T_{max}</math>, <math>C_{trough}</math> (AT-273 only))
 

### 3.2.3 Exploratory Endpoints

Exploratory endpoints corresponding to exploratory objectives are:

Exploratory objective	Exploratory endpoints

PD	
 
• Change in DENV viral load (as measured by infectious viral titre) from baseline
 
• Area under the log 10-transformed viral load curve (AUC) from first dose to the end of treatment or study [as measured by DENV RNA and viral titre]
 
• Time to viral load clearance, which is defined as the first of 2 consecutive undetectable viral load measurements [as measured by DENV RNA and viral titre]
 
• Time to clearance of NS1 protein using a NS1 antigen test. Clearance is defined as time from start of treatment until the first of 2 consecutive plasma samples are NS1-negative.
 
• Subgroup analysis by DENV serotype: Change of DENV viral load [as measured by DENV RNA and viral titre] from baseline, viral load AUC, time to viral load, or NS1 clearance by DENV serotype
 
• Treatment-emergent amino acid substitutions in DENV NS5 polymerase
 
• Time to resolution or duration of fever
 
• Exploratory biomarkers on immunological response to dengue (See list in Section 12)
 
• Exploratory analysis to evaluate exposure-response relationship. The relationship between the exposure of AT-752 (and its metabolites) and DENV viral load measurement may be explored using graphic displays.
 

----	--

#### 4. General Statistical Considerations

All statistical analyses will be conducted using statistical analysis system SAS® Version 9.4 or higher (SAS Institute, Cary, NC).

Analysis of the data from this study will be descriptive in nature. Confidence intervals and p-values will be descriptive due to small sample size in this study. N, mean, standard deviation, median, minimum and maximum, and 95% CI will be used for continuous data and number and percentage

will be used for categorical/count data, unless specified otherwise. No analysis will be performed until the data are unblinded.

All tables, listings, and figures will be presented by assigned treatment. The treatments below will be used for presentations:

- AT-752 750 mg TID
- AT-752 up to 1000 mg BID or TID
- AT-752 up to 1500 mg BID
- Placebo (pooled Cohort 1 through Cohort 3)

All data listings will be sorted by treatment and subject number. If a regimen is repeated in more than one cohort, the matching cohorts will be pooled as one treatment.

Unless otherwise specified, no algorithm for imputation of missing data will be employed.

Study days are calculated with respect to the first date of study drug exposure (First Dose Date) as below:

- If the assessment/observation date is on or after the first dose date, then  
Study Day = Assessment/Observation Date – First Dose Date + 1;
- Otherwise, Study Day = Assessment/Observation Date – First Dose Date

Baseline will be defined as the last non-missing assessment (including repeated and unscheduled assessments) before administration of the first dose of study drug, unless otherwise specified.

For summary of safety assessments, if there are repeated measurements at a time point, the first non-missing assessment at that time point will be used in the summary tables.

Unscheduled results will not be included in the summary tables, except for determining baseline, but will be presented in data listings.

The methodology and data handling specifications for PK data are detailed in Section 11.

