### **8.3.3 Safety Analyses**

Adverse events will be coded by preferred term and system organ class using the latest version of the MedDRA. Severity of AEs will be graded according to the grading scales modified from DAIDS Table for Grading the Severity of Adult and Pediatric Adverse Events (DHHS 2017). All AE data will be presented in a data listing. Treatment-emergent AEs will be summarized by treatment and overall, as well as by severity and relationship to study drug. Serious AEs and AEs leading to discontinuation of study drug will also be presented in the data listings and summarized by treatment and overall.

Relevant laboratory, vital sign (pulse rate, respiratory rate, blood pressure, and temperature), and ECG data will be displayed by time. Where appropriate, graded laboratory abnormalities will be summarized by treatment (DHHS 2017). Shift tables will be generated to summarize baseline and post-baseline severity grades. Physical examination findings will be presented in a data listing.

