#### **4.3. Analysis Population**

Primary endpoint analyses will be applied to the modified intent-to-treat population (mITT), which is defined as all randomized subjects who received at least 1 dose (full dose, unless assigned to placebo) of study drug (AT-752 or matching placebo) and have baseline and at least one post-baseline virology measurement. Change from baseline viral load (DENV RNA) will be compared between each AT-752 arm and a combined placebo group.

As-treated population is defined as all subjects who received at least 1 dose (full dose, unless assigned to placebo) of study drug (AT-752 or matching placebo) based on the actual treatment the patients received and had baseline and at least one post-baseline virology measurement.

The safety population will include all subjects who receive at least 1 dose of study drug.

The PK population will include all subjects who receive at least 1 dose of AT-752 and have sufficient concentration data to support accurate estimation of at least 1 PK parameter. PK parameter summaries will include only subjects in the PK population who have sufficient concentration measurement data to support estimation of the parameter. All subjects excluded from the PK population will be documented in the data listings.

The PD population will be the mITT population, which includes subjects who received at least 1 dose (full dose, unless assigned to placebo) of study drug and have baseline and at least 1 post-baseline viral load measurement.

The Per Protocol (PP) population will include the subset of the modified intent-to-treat population who completed study drug treatment without a major protocol violation that impact patient safety or data quality.

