### 8.1.2 Primary Endpoint Supportive Analyses

The primary endpoint will also be analyzed using the same method in the as-treated population.

The following viremia descriptively summarized by treatment arm, with comparison method indicated in parentheses:

- Change from baseline in log10 viral load by scheduled time point (Kruskal-Wallis). Along with the Kruskal-Wallis test, a one-way ANOVA will be used to compare treatment effect separately at each time point.
- Proportion of measurements above the lower limit of quantification (Fisher exact)

All viremia data will be listed and individual profiles of viremia over time will be presented for each subject. Viremia levels below the lower limit of quantification will be considered as 0 in the log10 viral load summaries and indicated as BLQ in the listings.

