## 9. Safety Analysis

All safety summaries and analyses will be based upon the safety population. Summaries will be presented by treatment group and overall.

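### The SAP displays safety outputs by assigned rather than received treatment, so a mis-dosed patient's adverse events would be tabulated under a treatment the patient did not take

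*SAP*

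**What the plan says.** The general rule is in SAP Section 4: "All tables, listings, and figures will be presented by assigned treatment". The display columns listed under it are the three AT-752 regimens and one placebo column pooled over the cohorts. Elsewhere in Section 4, the rules on descriptive statistics, imputation and baseline each allow for exceptions specified elsewhere. This sentence does not.

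Three passages bear on safety:

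- SAP Section 4.3: "The safety population will include all subjects who receive at least 1 dose of study drug". Nothing says how those subjects are grouped. Protocol Section 8.2 has the same definition and the same silence.
- SAP Section 9: "All safety summaries and analyses will be based upon the safety population", and then "Summaries will be presented by treatment group and overall". Treatment group is not defined there as assigned or received.
- Protocol Section 8.3.3: "Treatment-emergent AEs will be summarized by treatment and overall, as well as by severity and relationship to study drug". Again, assigned or received is not specified.

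Actual treatment does appear in two other places:

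- SAP Section 4.3 defines an as-treated population "based on the actual treatment the patients received and had baseline and at least one post-baseline virology measurement". Its one stated use is in Section 8.1.2: "The primary endpoint will also be analyzed using the same method in the as-treated population".
- Membership of the PK population (SAP Section 4.3) requires at least one dose of AT-752. Section 11 restricts PK listings and individual profiles to safety-population subjects treated with AT-752.

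**The concern.** Safety tables are meant to show what happened to patients exposed to each treatment. Under the Section 4 rule, a placebo-assigned patient who took AT-752 appears in the placebo column, and an active-assigned patient who took placebo appears in an AT-752 column. If the drug causes an event, both errors on average pull the columns together.

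Safety against placebo is a secondary objective. Protocol Section 1.2.1 reports that gastrointestinal events were more common on AT-752 than on placebo in the healthy-volunteer study, and that vomiting appeared to increase with dose level. That is the contrast at stake. With about 15 patients per column, one misplaced patient is visible.

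The SAP also treats the same patient inconsistently. A placebo-assigned patient who took AT-752 would move to the active group in the as-treated viral load analysis and could enter the PK population. The same patient's adverse events, and any PK table covered by the Section 4 rule, would still sit under placebo.

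**Working it through.** **Step 1: which rule governs the safety tables.**

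| Place | What it fixes | Does it override Section 4? |
|---|---|---|
| SAP 4 | All outputs by assigned treatment | It is the rule |
| SAP 4.3, safety population | Who is included: at least one dose | No, silent on grouping |
| SAP 9 | Safety population; by treatment group | No, group not defined as received |
| Protocol 8.2 and 8.3.3 | Same inclusion; by treatment | No, silent |
| SAP 4.3 and 8.1.2, as-treated | Actual treatment, virology data required | Only for viral load |
| SAP 4.3 and 11, PK | Membership depends on receiving AT-752 | Only for who enters the PK outputs |

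A programmer following the text would group adverse events by assigned treatment. The as-treated population cannot stand in for the safety set, because it drops subjects without baseline and post-baseline virology.

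**Step 2: column sizes.** SAP Section 3.1 plans 15 AT-752 and 5 placebo per cohort. Three cohorts give a pooled placebo column of 3 × 5 = 15. The plan states no figure for the effect of mis-dosing, so there is none to reproduce. Its power figures for the same group sizes do reproduce: for 1 log10, SD 1.25 and a one-sided 0.10 t-test, 81.0% at 15 versus 15 (stated 80%) and 59.2% at 15 versus 5 (stated 59%). They do not depend on this point.

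**Step 3: weight of one patient.** In a row where the mis-dosed patient has the event, that patient contributes 1/15 = 6.7 points to the assigned column. Where the patient does not have the event, only the denominators change. For example, 3/15 = 20.0% becomes 3/16 = 18.75%, a shift of 1.25 points.

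**Step 4: effect on the contrast.** The event counts are assumptions. One placebo-assigned patient takes AT-752 and has the event. Let a be the number of events among the 15 active-assigned patients and p the number among the other 14 placebo-assigned patients.

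- By assigned treatment: a/15 − (p + 1)/15
- By received treatment: (a + 1)/16 − p/14

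| a, p | By assigned | Difference | By received | Difference |
|---|---|---|---|---|
| 3, 0 | 3/15 = 20.0% vs 1/15 = 6.7% | 13.3 | 4/16 = 25.0% vs 0/14 = 0% | 25.0 |
| 7, 3 | 7/15 = 46.7% vs 4/15 = 26.7% | 20.0 | 8/16 = 50.0% vs 3/14 = 21.4% | 28.6 |

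In the first example the active column itself moves by 25.0 − 20.0 = 5.0 points, not 6.7, because its denominator grows.

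**The case against.** The strongest reply is that this is a wording gap with little practical effect. Section 4 is a general section, and a specific population definition would normally take precedence, so the as-treated analysis does not really conflict with it. That is fair for viral load. It does not help safety, because no specific rule for safety exists to take precedence.

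A mis-dosed patient would also not be hidden. SAP Section 7.3 lists dosing, Section 5.2 lists all protocol deviations and summarizes the important ones, and Section 9.1 lists all adverse events. In a trial of about 60 subjects a reader could trace the case. This softens the consequence but leaves the summary tables wrong.

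Several stronger readings are tempting, and the documents do not support them:

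- *The sponsor expects misallocation, since it created an as-treated set.* The SAP states no expectation, count or error rate. Such a set is an ordinary contingency.
- *Actual treatment is used only in the as-treated set.* PK membership also depends on receiving AT-752.
- *One error moves 6.7 points in every safety table.* Step 3 shows that this applies only to rows where the patient has the event. The overall column does not change.
- *Cohort escalation decisions would be distorted.* Protocol Section 5.1.1 bases them on unblinded safety summaries reviewed by the Safety Review Committee. No visible text says that those summaries follow the SAP rule, and much of that section is redacted.

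**Conclusion.** The point holds as a minor correction. Read literally, the SAP assigns a mis-dosed patient's adverse events to a treatment the patient did not take. This is a stated rule that gives the wrong grouping, not merely missing detail.

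The size is conditional. With no dosing error, the assigned and received groupings coincide and nothing changes. Parts of the treatment-assignment section (Protocol Section 5.3) are redacted, so the likelihood of an error cannot be judged. With one error, the assumed examples shrink the active-placebo difference from 25.0 to 13.3 points or from 28.6 to 20.0 points. They rest on invented event counts and on the planned 15-patient columns. SAP Section 4 pools cohorts that repeat a regimen; such a column would hold 2 × 15 = 30, and one patient would weigh 1/30 = 3.3 points.

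The analyses are declared descriptive, so no safety test or decision threshold is affected. The consequence is firmest for the final safety tables, which can inform dose selection for later trials (SAP Section 1).

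**What to change.** In SAP Section 4, limit the assigned-treatment sentence to mITT and per-protocol outputs, and state that safety, PK and as-treated outputs are presented by treatment actually received. Repeat the received-treatment rule in Section 4.3, under the safety population, and in Section 9.

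Add a classification rule for a subject who received both AT-752 and placebo. Treatment runs to 10 or 15 doses, so an error could affect only some of them, and treatment received is then undefined. One workable convention counts any subject who took at least one dose of AT-752 under AT-752. Its cost is that a briefly exposed subject counts fully as active, so a footnote should identify such cases. Fix the rule before unblinding, so that it is not chosen with knowledge of who had which events.

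The cost is a few sentences and one treatment-received variable in the analysis datasets. Sample size, power and alpha are unchanged. The protocol does not specify assigned or received treatment for safety, so the change contradicts nothing in it.

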#### **4.1. Sample Size**

The sample size for this study is up to 60 subjects and each cohort will include 20 subjects, allocated 3:1 (AT-752:placebo). In Low et al (Low 2014), the observed standard deviations (SD) for VLR, defined as mean change from baseline viral load on days 2,3, and 4, ranged from 0.75 (N=26) to 1.07 (N=24). Taking into account that the VLR endpoint in the study was based on an average of 3 measurements and assuming that there is some correlation between measurements on days 2 through

4, we consider power to detect a true effect at a single time point using a one-sided 0.10 level test (unadjusted for multiple comparisons) with N=15 per arm for SD in a range from 1 to 1.75:

True standard deviation	Effect (log 10 copies/ml) with 80% power (N=15 vs. 15)	Effect (log 10 copies/ml) with 80% power (N=15 vs. 5)
1	0.8	1.1
1.25	1	1.4
1.5	1.2	1.7
1.75	1.4	2.0

Based on the above table, there is 80% power to detect a true treatment effect (versus placebo) on change-from-baseline viral load of 1 log10 at a time point if the true SD is 1.25 for comparison of groups with N=15 each. The analogous power to detect a 1 log10 effect for a within cohort comparison is 59%. Furthermore, if true SD is in the range from 1 to 1.75, the probability that the observed effect would be 0.5 log10 or larger is low (in range from 0.09 to 0.22) if there is no treatment effect, i.e., an observed effect of 0.5 or larger might be considered suggestive of a signal. Interpretation of results will consider the totality of the data.

In the event there is at least one subject who withdraws without post-baseline virology data, with the exception of those who withdraw for safety or tolerability, enrollment may remain open or extended at each dose level/cohort to enroll additional randomization block(s) of 4 patients (3:1) to increase the likelihood that at least 15 active and 5 placebo subjects with evaluable virology data are included in each cohort. Any additional patients will be randomized through the same centralized randomization process. All statistical analysis will be based on actual enrolled subjects.

#### 4.2. Randomization, Stratification, and Blinding

The randomization schedule will be generated prior to the initiation of the study. Subjects who meet all inclusion and none of the exclusion criteria will be randomly assigned in a 3:1 ratio to either experimental drug or placebo. Randomization will be stratified by geographic region. Randomization numbers (in sequential order) will be assigned before the first dose of study drug is administered on Day 1. This is a double-blind study: the investigator and the subject will be kept blinded to the treatment allocation.

#### **4.3. Analysis Population**

Primary endpoint analyses will be applied to the modified intent-to-treat population (mITT), which is defined as all randomized subjects who received at least 1 dose (full dose, unless assigned to placebo) of study drug (AT-752 or matching placebo) and have baseline and at least one post-baseline virology measurement. Change from baseline viral load (DENV RNA) will be compared between each AT-752 arm and a combined placebo group.

As-treated population is defined as all subjects who received at least 1 dose (full dose, unless assigned to placebo) of study drug (AT-752 or matching placebo) based on the actual treatment the patients received and had baseline and at least one post-baseline virology measurement.

The safety population will include all subjects who receive at least 1 dose of study drug.

The PK population will include all subjects who receive at least 1 dose of AT-752 and have sufficient concentration data to support accurate estimation of at least 1 PK parameter. PK parameter summaries will include only subjects in the PK population who have sufficient concentration measurement data to support estimation of the parameter. All subjects excluded from the PK population will be documented in the data listings.

The PD population will be the mITT population, which includes subjects who received at least 1 dose (full dose, unless assigned to placebo) of study drug and have baseline and at least 1 post-baseline viral load measurement.

The Per Protocol (PP) population will include the subset of the modified intent-to-treat population who completed study drug treatment without a major protocol violation that impact patient safety or data quality.

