### **3.1.2 Timing of TID Dosing**

If possible, the first dose of study medication should be administered on the same day as screening.

The first dose of study medication (on Day 1) must be taken under observation at the study site. All other doses will be administered at the study site for subjects who are confined to the site during the study, or will be self-administered outside the study site (e.g., at home) for subjects at sites that choose to use mobile nursing (except the doses administered prior to PK evaluation [Dose 7, 8, or 9; see [Section 3.1.4](#)], which must be taken under observation at

the study site, or under observation by mobile nursing staff as applicable). The timing of the doses will be recorded in a patient diary.

The first dose of study medication should be administered between 6 AM and 4 PM, inclusive or between 8 PM and 10 PM, inclusive. Dosing after 4 PM but before 8 PM would make scheduling for the second dose difficult, considering the later hours.

The second dose of study medication must be taken after at least 6 hours and no later than 10 hours after the first dose, allowing the participant to select a convenient 8-hour ( $\pm 2$  hours) dosing schedule thereafter to complete a total of 15 doses.

For example, if a patient intends to choose a 6 AM, 2 PM, 10 PM dosing schedule:

- Then if the first dose is administered between 6 AM and 8 AM on Day 1, the second dose should be administered at 2 PM on Day 1 and the third dose at 10 PM on Day 1, and the subject can then proceed with the 6 AM, 2 PM, and 10 PM dosing schedule on Day 2 and thereafter.
- Or if the first dose is administered between 8 AM and 10 AM on Day 1, the second dose should be administered at 4 PM on Day 1 and the third dose at 10 PM on Day 1, and the subject can then proceed with the 6 AM, 2 PM, and 10 PM dosing schedule on Day 2 and thereafter.
- Or if the first dose is administered between 10 AM and noon on Day 1, then the second dose should be administered at 8 PM on Day 1, and the subject can then proceed with the 6 AM, 2 PM, and 10 PM dosing schedule on Day 2 and thereafter.
- Or if the first dose is administered between noon and 4 PM on Day 1, the second dose should be administered at 10 PM on Day 1, and the subject can then proceed with the 6 AM, 2 PM, and 10 PM dosing schedule on Day 2 and thereafter.

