## 8.2 ANALYSIS SETS

The analysis populations are as follows:

- The primary analysis population is the modified intent-to-treat (mITT) population, which will include all randomized subjects who received at least 1 dose of study drug and have baseline and at least 1 post-baseline virology measurement. The primary analysis will also be performed on the per-protocol population of patients who completed treatment without a major protocol deviation.

- The PK population will include subjects who receive at least 1 dose of the study drug and have sufficient concentration data to support accurate estimation of at least 1 PK parameter.
- The safety population will include all subjects who receive at least 1 dose of study drug.
- A per protocol population will include the subset of the modified intent-to-treat population who completed study drug treatment without a major protocol violation.

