## **8. Efficacy**

Primary efficacy endpoint analyses will be applied to the modified intent-to-treat population, which is defined as all randomized subjects who received at least 1 dose of study drug and have baseline and at least one post-baseline virology measurement. The primary analysis will also be performed on the per-protocol population of patients who completed treatment without a major protocol deviation.

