### 14. Changes in the Planned Analysis

There are no changes to the planned analyses described in the protocol.

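### SAP 4.3 requires a full dose for entry to the primary population on AT-752 but not on placebo, contradicting SAP 8 and Protocol 8.2

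*SAP*

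**What the plan says.** SAP 4.3 (Analysis Population) defines the mITT population as "all randomized subjects who received at least 1 dose (full dose, unless assigned to placebo) of study drug (AT-752 or matching placebo"), with baseline and at least one post-baseline virology measurement. The same parenthetical condition is repeated in the as-treated and PD definitions. The per-protocol population is the "subset of the modified intent-to-treat population who completed study drug treatment without a major protocol violation", so it takes the condition over from mITT.

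SAP 8 (Efficacy), describing the population for the same primary analysis, has no such condition: "all randomized subjects who received at least 1 dose of study drug and have baseline and at least one post-baseline virology measurement". Protocol 8.2 agrees: "all randomized subjects who received at least 1 dose of study drug and have baseline and at least 1 post-baseline virology measurement". The Statistical Methods part of the protocol synopsis uses the same definition as Protocol 8.2.

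SAP 14 states: "There are no changes to the planned analyses described in the protocol". Neither document explains why a full dose is required in one arm only, and neither defines a full dose for this purpose.

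**The concern.** There are two separate problems.

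- **Two definitions, no precedence.** SAP 4.3 and SAP 8 cannot both govern, and nothing says which prevails. SAP 4 allows no analysis before unblinding, and SAP 13 and Protocol 5.4.1 allow the sponsor unblinded reviews during the study. A choice left open until then could be made with results in view.
- **Arm-dependent membership.** If 4.3 governs, two subjects with the same partial intake and the same virology data are treated differently according to assignment. Selecting on post-randomisation behaviour in one arm only can bias the AT-752 versus placebo comparison. Membership also cannot be fixed under the blind.

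The planned supportive analyses would not reveal or undo the effect. The as-treated set repeats the condition, and does so awkwardly: the set is built on treatment actually received, but the waiver depends on assignment. The per-protocol set is a subset of mITT and also requires completed treatment. The additional enrolment in SAP 4.1 is triggered by "at least one subject who withdraws without post-baseline virology data", so a subject excluded for partial intake, who has virology data, does not trigger it.

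**Working it through.** **1. Who is affected.** The definitions differ only for a subject assigned to AT-752 who took part of a dose, never took a full one, and has baseline and post-baseline virology.

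| Subject | SAP 4.3 | SAP 8 and Protocol 8.2 |
|---|---|---|
| AT-752, partial intake only, virology available | Excluded | Included if a partial dose counts as a dose |
| Placebo, same intake, virology available | Included | Included on the same terms |
| Either arm, one full dose at any time | Included | Included |

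**2. Whether a partial dose is possible.** SAP 7.3 gives 250 mg tablets and expected totals of 45, 40, 60 and 60 tablets for 750 mg TID, 1000 mg BID, 1000 mg TID and 1500 mg BID. Over 15, 10, 15 and 10 doses that is 45/15 = 3, 40/10 = 4, 60/15 = 4 and 60/10 = 6 tablets per dose. Protocol 1.2.1 reports that vomiting in healthy subjects appeared to increase with AT-752 dose level from 750 mg upward. Incomplete intake is therefore possible and could be related to treatment. The documents give no rate.

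**3. The plan's own figures.** Inputs from SAP 4.1: one-sided 0.10, SD 1.25, effect 1 log10. With the noncentral t:

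- 15 vs 15: SE = 1.25×sqrt(1/15+1/15) = 0.456; power 0.810 (stated 80%).
- 15 vs 5: SE = 1.25×sqrt(1/15+1/5) = 0.645; power 0.592 (stated 59%).

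Both reproduce. If 1, 2 or 3 of the 15 active subjects were removed, power against 15 pooled placebo would be 0.799, 0.787 or 0.773. The loss of precision is small, about one percentage point per subject. Selection matters more.

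**4. Possible bias.** Let k of 15 active subjects be excluded and let their mean change differ from that of the retained subjects by g log10. The full active mean is [(15−k)×retained + k×excluded]/15, so dropping the k subjects shifts the active mean by k×g/15. With SE = 1.25×sqrt(1/(15−k)+1/15), the nominal one-sided 0.10 error becomes 1 − Φ(1.2816 − bias/SE) when the excluded subjects had less decline.

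| k (assumed) | g (assumed) | Bias, log10 | SE | Nominal 0.10 becomes |
|---|---|---|---|---|
| 0 | – | 0 | 0.456 | 0.100 |
| 1 | 0.5 | 0.033 | 0.465 | 0.113 |
| 2 | 1.0 | 0.133 | 0.474 | 0.159 |
| 3 | 1.5 | 0.300 | 0.484 | 0.254 |

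The noncentral t gives 0.251 for the last row. If the excluded subjects had more decline, the last row becomes 1 − Φ(1.2816 + 0.300/0.484) = 0.029.

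The values of k and g are illustrations; the documents support none in particular. The error column assumes no drug effect, so g there must be prognostic: poorer exposure alone creates no difference when the drug does nothing. The calculation ignores the baseline viral load covariate in SAP 8.1.1, which could absorb part of a prognostic difference.

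**The case against.** The strongest reply is that the affected group is close to empty. Protocol 3.1.2 says "The first dose of study medication (on Day 1) must be taken under observation at the study site", and 3.1.3 has the same requirement for BID dosing. The doses used for serial PK sampling are also observed. A subject would have to miss a full dose on every one of 10 or 15 occasions and still provide post-baseline virology. In Phase 1, all but one subject, who withdrew consent, completed the study. This stands, and it is why the effect may be nil.

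Second, no formal decision depends on the 0.10 level: "Confidence intervals and p-values will be descriptive due to small sample size in this study". That also stands, and it limits what the error column means. It does not remove bias from the point estimate, which is what would be read for a signal.

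Third, exclusions would be visible in the population counts by treatment (SAP 5.1), the exposure summaries and dosing listing (SAP 7.3) and the viremia listings and profiles (SAP 8.1.2). True, but these do not say which definition is primary.

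Fourth, the per-protocol point has little practical weight, since anyone who completed treatment will almost certainly have taken a full dose. Agreed.

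Fifth, the condition may only clarify what counts as a dose, which the protocol leaves open, and a full dose in milligrams has no meaning for a placebo tablet. That could explain a full-dose rule on active drug. It does not explain exempting placebo, because placebo tablets can be counted in the same way (SAP 7.3 measures dose in tablets), nor why SAP 8 omits the condition.

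**Conclusion.** The concern holds. The text mismatch is certain: SAP 4.3 conflicts with SAP 8, Protocol 8.2 and the synopsis on the primary population, SAP 14 does not acknowledge it, and the 4.3 version depends on assigned arm together with post-randomisation intake. The numerical effect is uncertain and may be zero. Under the assumed values it runs from 0 to 0.30 log10, against the 0.5 log10 that SAP 4.1 says might be considered suggestive of a signal, and its direction depends on how the excluded subjects fared. This should be fixed because it concerns the primary population and costs almost nothing to correct, not because a large bias has been shown.

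**What to change.** Delete the parenthetical full-dose condition from the mITT, as-treated and PD definitions in SAP 4.3, so that mITT matches SAP 8 and Protocol 8.2 and the SAP 14 statement is true on this point.

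Separately, state in the SAP whether an incomplete multi-tablet dose counts as a dose for population membership. The rule must be identical in both arms and fixed before unblinding. Protocol 8.2 does not settle this.

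The cost is SAP wording only: no added subjects and no change to any stated power figure. Any poorly exposed AT-752 subjects who return to the primary analysis may make the estimate slightly less favourable.
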